## **Study protocol**

**Participants:** We aim to recruit a total of 120 participants (60 for the intervention and 60 as a control group).

Inclusion criteria include any gender, age between 40 and 89 years old, illiteracy (TOFHLA score <53) and availability to participate in the study for at least 12 months.

Exclusion criteria will be: A) Presence of remarkable cognitive complaints and/or decompensated psychiatric illness (depression and anxiety) and/or current substance abuse such as alcohol and illicit drugs use. B) Objective cognitive impairment: 2 standard deviations or less for age and education on the Mini-Mental State Evaluation (MMSE) and/or 6 or less points on the delayed recall task from the Brief Cognitive Battery. C) History of previously diagnosed dyslexia D) Formal MRI contraindications including metal or claustrophobia. E) Severe structural lesions detected by MRI.

Informed consent will be written in accessible language and collected using the approach “teach-to-goal developed for vulnerable populations.

First, we will do pair matching with the 120 participants dividing them into two clusters paired for age, sex and baseline non-verbal intelligence and literacy level (by TOFLHA). Next, within each pair, one cluster is randomized to receive the intervention (n=60), and the other cluster receives the placebo (n=60). Based on our pilot project and historical data, we calculate an attrition rate of 20%. Thus, the final sample is expected to have 96 individuals. We will reassess the participants’ cognition and neuroimaging after 6 months.

**Literacy and cognitive reserve assessment:** Reading comprehension and numeracy skills will be evaluated using the Test of Functional Health Literacy in Adults (TOFHLA) that has been validated for Brazilian Portuguese. A score of or lower 53 defines illiteracy. Global cognitive reserve will be assessed with a structured questionnaire available in Portuguese, that includes years of education, leisure activities and occupational attainment. Sociodemographic features, the level of physical exercise, smoking, and alcohol habits, as well as the presence of psychiatric illness, will be addressed with specific questionnaires.

**Cognitive evaluation:** Includes the MMSE, the Brief Cognitive Battery, and the Free and Cued Selective Reminding with Immediate Recall (FCSR-IR). The first two tests will assess global cognition and will be used as a screening for the presence of baseline cognitive impairment. The FCSR-IR includes a controlled learning phase, which provides the basis for encoding specificity and effective cued recall. The FCSR-IR Free Recall sum-of-attempts will be the proxy for episodic memory. We will also test other cognitive abilities than episodic memory such as non-verbal intelligence (Beta-3 test), attention (digit span), reading abilities (Human Frontier Science Program reading test), words and sentence repetition, rapid naming of colors, letters, numbers, and objects and verbal comprehension (Token test). Although scores for all tests described are known to be affected by literacy level, this effect will be accounted for because our participants will all have a low literacy level.

**Neuroimaging acquisition and analysis:** We will use the ADNI-3 protocol to acquire Diffusion tensor Imaging (DTI), resting-state functional MRI (rsfMRI), Fluid Attenuation Recovery and 3D-T1 images pre-and post-intervention in a 3T Siemens Verio scanner. For the rsfMRI analysis, a filter will be applied to attenuate noise frequencies of raw signal. We will then place a seed in the right and left hippocampus (HC) with an automated atlas that will be used to assess coherent blood oxygen level-dependent activity (BOLD) between this region and the ventral medial prefrontal cortex, corresponding to the HC-VMPFC intrinsic

functional connectivity (iFC). Both HC and VMPFC will be used in the region of interest (ROI) analyses, and ROI-averaged values for iFC and gray matter values will be calculated pre- and post-intervention.

**Literacy training (intervention):** The basic-literacy training will be given for 6 months. At baseline, participants will be randomized into four classes of 30. Co-I [name], who is an expert in adult education, will oversee the classes and meet the teachers periodically, and each class will count with a certified and experienced lead teacher and teacher aid. Two of the classes of 30 each will be the intervention group. They will receive literacy training based on analytical and phonemic methods for enabling reading and writing. The two other classes of 30 each will be the placebo group. The placebo group will have access to non-literacy classes offered at the adult school, including geography, history, informatics, and sciences, but no literacy-training.

Both the intervention and the placebo groups will attend classes of two hours/day for four days/week. The teachers will record attendance. The follow-up neuroimaging and neuropsychology testing will be done at the 6 months mark. The informed consent will have a session explaining that participants will be randomly assigned to participate in the intervention or placebo group in the first 6 months so that they will be blind to which group they were assigned for at baseline. Based on the literacy-program experience, we expect a dropout rate of 20%. Thus, we expect to have 96 participants concluding the study. Participants who drop out will be monitored by phone calls every three months and will be also reassessed after 6 months, if interested. We will compare the dropout group with the groups that kept the training to see whether there were differences in intelligence or sociodemographic aspects.

**Blood samples:** At the baseline, we will collect blood samples of participants to assess the apolipoprotein E genotype. Upon participant consent, plasma and serum samples will be stored for future analysis of potential peripheral markers associated with cognitive reserve.

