Better Memory with Literacy Acquisition Later in Life

NCT number NCT04473235

Date April, 29th 2024

Statistical analysis plan

Primary outcome:

The episodic memory will be measured using the Free and Cued Selective Reminding test (FCSRT). This test has 3 steps. First, the participant learns 16 figures, 4 each, with the help of semantic cues. After learning the first 16 figures, the participant recalls them three times, with distraction activity between each attempt (counting 20 to 1 backwards). The sum of each immediate free recall is called sum of attempts. It ranges from 0 (the participant does not recall any of the 16 figures in three attempts) to 48 (the participant recalls all the figures). We used this score as a measurement of episodic memory for the primary outcome.

The total raw score on the free recall sum-of-attempts trial from the FCST at the 6 months of follow up will be subtracted by the same score at baseline, in the intervention and control groups. The mean difference in each group will be compared using a paired T-test.

Secondary outcome:

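### Pairs are not matched on baseline FCSR-IR free recall, which leaves avoidable chance imbalance and some lost precision in the primary change score

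*Protocol*

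**What the plan says.** Protocol, Participants: the 120 participants are divided into pairs "paired for age, sex and baseline non-verbal intelligence and literacy level" (measured by TOFHLA), and then "within each pair, one cluster is randomized to receive the intervention (n=60), and the other cluster receives the placebo (n=60". Attrition of 20% is expected, so "the final sample is expected to have 96 individuals".

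Protocol, Cognitive evaluation: "The FCSR-IR Free Recall sum-of-attempts will be the proxy for episodic memory". The Beta-3 test, which supplies the non-verbal intelligence score used for matching, is in the same battery.

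SAP, Primary outcome: the baseline free-recall sum (range 0 to 48) is subtracted from the 6-month sum, and "The mean difference in each group will be compared using a paired T-test". No covariate is named for this outcome. Age is named as a covariate only in the text on the MRI outcome.

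**The concern.** Matching before randomisation helps a trial to the extent that the matched factors predict the endpoint. Here the endpoint is a change score. A factor that shifts the baseline and 6-month scores by the same amount cancels when one is subtracted from the other, so matching on it does little for the precision of change. The protocol says that literacy affects test scores, which is a statement about level. Neither document links any of the four matching factors to change.

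Baseline free recall differs in this respect. It is part of the endpoint and is related to change through regression to the mean: the arm that happens to start lower tends to gain more. It must be measured at baseline in any case. Leaving it off the list, with no baseline term in the analysis, means that a chance difference in starting memory passes partly into the treatment contrast, and that the contrast is less precise than the same 60 pairs could give.

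**Working it through.** **The plan's own figure.** 120 x (1 - 0.20) = 96, or 48 per arm if dropout is equal. This reproduces. The documents give no SD, effect size, power or correlation, so there is no stated precision to check.

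**Assumptions.** Equal SDs at both visits. The baseline to 6-month correlation r is set at 0.4, 0.6 and 0.8. In the simulations 120 people form 60 pairs by multivariate distance, with sex weighted heavily. Where a value is needed, the continuous matching factors explain about 24% of baseline free-recall variance.

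**1. How baseline relates to change.** In units of the score variance, Var(change) = 2(1 - r) and Var(change given baseline) = 1 - r^2. Their ratio is (1 + r)/2, and corr(change, baseline) = -sqrt((1 - r)/2).

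| r | corr(change, baseline) | ratio | reduction |
|---|---|---|---|
| 0.4 | -0.55 | 0.70 | 30% |
| 0.6 | -0.45 | 0.80 | 20% |
| 0.8 | -0.32 | 0.90 | 10% |

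These are the reductions from exact matching on baseline free recall alone. If the other four factors are also matched, and they act on level but not on change, the ceiling is higher: (1 - r)/(2 x 0.76) = 39%, 26% and 13%. Imperfect matching pulls the result back below that.

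**2. Simulated matching, all 60 pairs intact.**

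| r | within-pair correlation of change, present list | with free recall added | variance reduction |
|---|---|---|---|
| 0.4 | about 0 | 0.25 to 0.31 | 26-31% |
| 0.6 | about 0 | 0.16 to 0.19 | 17-21% |
| 0.8 | about 0 | 0.07 to 0.10 | 5-12% |

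The zero in the second column depends on the four factors not predicting change. With an age-change correlation of -0.4, the present list gives about 0.12 to 0.15. In a separate calculation at r = 0.7, with perfectly matched factors explaining 30% of baseline variance, the value was 0.02 or 0.13 when their effect at 6 months was 0.8 or 0.5 times the baseline effect. The variance reductions in the last column include scenarios in which age predicts change.

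The cost is that the mean within-pair age gap rises from about 0.38 to 0.46 SD, and sex mismatches from about 2% to 3% of pairs if sex is weighted rather than matched exactly.

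**3. Baseline balance.** The SD of the chance difference between arms is sqrt(2/60) x sqrt(1 - m), where m is the within-pair correlation of baseline free recall.
- No matching: m = 0 gives 0.183 SD.
- Present list: m of about 0.24 gives 0.183 x 0.87 = 0.16 SD, a 95% range of +/-0.31.
- Free recall added: simulated 0.075 SD, a 95% range of +/-0.15.

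A baseline difference d shifts the change-score contrast by (1 - r) x d. For d = 0.16 this is 0.10, 0.06 and 0.03 SD at r = 0.4, 0.6 and 0.8. For d = 0.075 it is 0.045, 0.03 and 0.015 SD.

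**4. Dropout.** Independent 20% dropout leaves 60 x 0.8 x 0.8 = 38.4 complete pairs. In units of the change variance, with within-pair correlation c:
- pair-level test: 2(1 - c)/38.4
- two-sample test ignoring pairs: 2/48 = 0.0417

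With c = 0 the pair-level variance is 0.0521, an SE 12% larger than the two-sample value. With c = 0.28, 0.18 and 0.09 (r = 0.4, 0.6, 0.8) it is 0.0375, 0.0427 and 0.0474. Break-even is c = 1 - 38.4/48 = 0.20. So adding free recall improves the pair-level test at every r, but makes it better than ignoring the pairs only at the lowest r.

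The simple difference in mean change over all 96 completers also benefits. Its true variance is (2/48)(1 - 0.8c) = 0.0323, 0.0357 and 0.0387, against 0.0417 when c = 0. An ordinary two-sample SE would not show that gain.

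**The case against.** The strongest reply is that this is a design preference with an easier substitute. Adjusting the 6-month score for its baseline gives the same variance ratio, (1 + r)/2, uses every completer, and needs neither intact pairs nor a change to allocation. That is right, and it removes most of the precision argument. But the SAP does not plan such an adjustment. With one, matching would still give balance that does not rely on a linear model for a score bounded at 0 and 48.

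Dropout also stands as a limit: the largest reductions assume 60 complete pairs.

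The documents further leave the pairing itself unclear. The SAP does not say whether its paired test pairs matched participants or visits within a person. Under Literacy training the protocol says "At baseline, participants will be randomized into four classes of 30", without mentioning pairs. If the test pairs visits, the pair-level gain in the working does not apply. These passages need reconciling whatever is decided here.

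Two stronger readings are tempting. A reader might infer that the primary outcome is left unbalanced at baseline. The documents do not support this: allocation is randomised within pairs, so only chance imbalance remains, and the change score passes on only a share (1 - r) of it. A reader might also infer that the present matching adds almost no precision. That holds only if the matched factors act about equally at both visits. The documents give no such information, and the age range of 40 to 89 leaves room for age to predict change.

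**Conclusion.** The point holds as a modest one. Leaving baseline free recall off the matching list, with no baseline adjustment in the SAP, leaves chance imbalance of about 0.16 SD (one SD of the between-arm difference) where about 0.075 was attainable. It also gives up roughly 5% to 31% of the variance of the paired change-score estimate, depending on r. Those figures rest on an assumed r of 0.4 to 0.8, equal SDs, simulated matching and complete pairs. The gain is smallest when r is high, and dropout shrinks it for a pair-level test. It is a missed opportunity in the design: the randomised comparison remains valid, and no figure in the plan is wrong. The priority is optional.

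**What to change.** **If pairs are not yet formed:** in the protocol under Participants, add the baseline FCSR-IR free-recall sum to the matching list. Match exactly on sex and use one multivariate distance for age, Beta-3, TOFHLA and free recall. Require the baseline FCSR-IR to be completed before pairing. This costs a line or two of text and no extra test or visit, since the score is already needed to compute change. The downside is slightly looser matches on age, Beta-3 and TOFHLA.

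**If pairs already exist** (the SAP is dated April 2024, and the documents do not say): adjust the primary comparison for baseline free recall and report the achieved baseline difference between arms. This costs a sentence in the SAP and a row in the baseline table.

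### A paired t-test between arms would drop anyone with 6-month data whose matched partner has none; the SAP should define the pairs or use a model that keeps everyone

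*Protocol*

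**What the plan says.** **Size and attrition.** The protocol's Participants paragraph sets the enrolment: "We aim to recruit a total of 120 participants (60 for the intervention and 60 as a control group". It applies 20% attrition and concludes: "Thus, the final sample is expected to have 96 individuals". The Literacy training paragraph repeats the figure and shows what it counts: "Thus, we expect to have 96 participants concluding the study". It adds that people who drop out are followed by telephone and, where they are willing, reassessed at 6 months.

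**Matching and allocation.** The Participants paragraph says: "First, we will do pair matching with the 120 participants dividing them into two clusters paired for age, sex". Non-verbal intelligence and literacy are also matching factors. Then: "within each pair, one cluster is randomized to receive the intervention (n=60), and the other cluster receives the placebo (n=60". The Literacy training paragraph describes allocation differently and does not mention pairs: "At baseline, participants will be randomized into four classes of 30".

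**Analysis.** Under Primary outcome, the SAP forms each person's change in free recall from baseline to 6 months and then says: "The mean difference in each group will be compared using a paired T-test". The Secondary outcome section names the same test for the change in hippocampal-prefrontal connectivity.

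Neither document says what the pairs in the t-test are, or what happens to a participant whose match has no follow-up value.

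**The concern.** By the time the t-test is applied, the before-after difference has already been taken. Each person has one change score, and the remaining comparison is between arms. A paired test then needs a link between one person in each arm, and the matched pair is the only such link in the documents.

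A matched-pair t-test uses a pair only if both members have a 6-month value. A participant who attends throughout and is retested is left out if the partner is not retested. The number analysed is then set by intact pairs, not by completers, and the plan forecasts only completers.

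Two things are at stake. People with complete data may be left out of the primary comparison for a reason unrelated to their own follow-up. And because no rule is fixed in advance, exclusion, re-matching or a switch of test could be chosen after the data are seen.

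**Working it through.** **Inputs from the protocol:** 120 participants, 60 per arm; 20% attrition, not split by arm or by pair. **Assumed, because the documents do not say:** 60 person-to-person pairs; how dropout falls within pairs; the share of dropouts reassessed; two-sided 5% significance and 80% power for the precision comparison.

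**1. The plan's own figure.** 120 × (1 − 0.20) = 96. It reproduces exactly, as a count of completers.

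**2. Intact pairs, independent dropout, nobody reassessed.** 60 × 0.8 × 0.8 = 38.4 pairs, or 76.8 people. About 96 − 77 = 19 completers would be left out.

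**3. Dropout that clusters within pairs.** With within-pair dropout correlation φ, intact pairs = 60 × (0.64 + 0.16φ).

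| φ | Pairs | People |
|---|---|---|
| −0.25 (24 dropouts in 24 different pairs) | 36.0 | 72 |
| 0 | 38.4 | 77 |
| 0.2 | 40.3 | 81 |
| 0.5 | 43.2 | 86 |
| 1 (both members always leave together) | 48.0 | 96 |

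The end rows are the limits for exactly 24 dropouts: 60 − 24 = 36 pairs and 60 − 12 = 48 pairs. Unequal dropout by arm changes little: 10% and 30% give 60 × 0.9 × 0.7 = 37.8 pairs, 76 people.

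**4. Some dropouts reassessed (independent within pairs).** If a share s returns, the proportion without 6-month data is 0.20 × (1 − s).

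| s | No data | People with data | Intact pairs | People in intact pairs | Left out |
|---|---|---|---|---|---|
| 0 | 20% | 96 | 60 × 0.80² = 38.4 | 77 | 19 |
| 25% | 15% | 102 | 60 × 0.85² = 43.4 | 87 | 15 |
| 50% | 10% | 108 | 60 × 0.90² = 48.6 | 97 | 11 |

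Reassessment raises the number analysed, but the paired test still leaves out people who have data.

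**5. Precision.** In units of the SD of change, by normal approximation with 1.960 + 0.842 = 2.802:
- unpaired, 48 per arm: 2.802 × √(2/48) = 0.57
- 38.4 pairs, within-pair correlation ρ: 2.802 × √(2(1 − ρ)/38.4) = 0.64 at ρ = 0, 0.57 at ρ = 0.2, 0.45 at ρ = 0.5

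Break-even is at ρ = 1 − 38.4/48 = 0.20. With t-distributions, the detectable effects at ρ = 0 are 0.66 (38 pairs) and 0.578 (48 per arm), so break-even is 1 − (0.578/0.660)² = 0.23. Hence roughly 0.2 to 0.25.

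**The case against.** **The 96 is not wrong.** A reader might infer an arithmetic error, or a trial that falls short of its required size. The documents support neither. The figure reproduces, it is described as the number finishing the study, and no effect size, SD, significance level or power is attached to it. This objection stands in full.

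**The SAP does not say the test runs on matched people.** It might intend a before-after test within each arm, or *paired* might be a slip for a two-sample test; either would use all completers. The protocol also mixes *pair* and *cluster* and elsewhere allocates to four classes, so 60 individual pairs are themselves an inference. The ambiguity is real, but it does not rescue the text: a within-arm test does not compare the arms, and a slip means that the wrong test is named. The primary analysis needs correcting on every reading.

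**77 is not a fixed result.** A reader might take it as the analysable number. It requires person-to-person pairs, independent dropout and no reassessed dropouts. The protocol states none of these, and it provides for reassessing dropouts who are willing. It should be shown only as one scenario.

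**Fewer people need not mean less precision.** Matching on age, sex, non-verbal intelligence and literacy could induce enough correlation to offset the lost pairs. This stands: the documents give no correlation for change scores, so neither a loss nor a gain can be claimed.

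**Conclusion.** The point holds as a gap in the analysis specification. On the only reading that makes the stated test a between-arm comparison, people with 6-month data are excluded when their partner has none, and the plan has no rule for broken pairs.

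Assuming 60 individual pairs and 20% independent dropout with nobody reassessed, about 38 pairs (77 people) would enter against 96 completers. With exactly 24 dropouts the limits are 72 and 96, and the upper one is reached only if partners always leave together. With a quarter of dropouts reassessed, about 87 of 102 would enter. The effect on precision is undetermined: it is a loss below a within-pair correlation of roughly 0.2 to 0.25 and a gain above it.

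The matter should be settled because it concerns the primary comparison and is cheap to settle.

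**What to change.** **Preferred.** In the SAP's Primary outcome and Secondary outcome sections, replace the paired t-test with a linear model of the 6-month value on arm, baseline value and the matching factors (age, sex, non-verbal intelligence, literacy). Add pair as a random effect if individuals are randomized within pairs. Include everyone with a 6-month value, whether or not the partner has one and whether or not they completed the classes. The 96 can then stand unchanged as the expected number of completers.

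**If the paired test is kept.** Define the pair, state how broken pairs are handled, and say that the number analysed is intact pairs. Give the range above as scenarios; do not enter 77 as a forecast.

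**In either case,** reconcile the protocol's two descriptions of allocation, because the choice of random effect depends on which unit was randomized.

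**Cost.** A change of SAP method for two outcomes and slightly more analysis work. No additional participants or assessments are needed.

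### Low literacy at entry does not account for literacy's effect on 6-month test scores; confine that claim to baseline and adjust for baseline TOFHLA

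*Protocol*

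**What the plan says.** In the protocol's Cognitive evaluation section, the sponsor acknowledges that "scores for all tests described are known to be affected by literacy level" and then states that "this effect will be accounted for because our participants will all have a low literacy level". The tests described there include the primary episodic memory measure (FCSR-IR free recall), a reading test and rapid naming of letters.

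Other parts of the two documents bear on that sentence:

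- **Entry (Protocol, Participants).** The inclusion criterion is "illiteracy (TOFHLA score <53", an upper limit with no lower limit given. The literacy assessment section words the limit differently: "A score of or lower 53 defines illiteracy".
- **Allocation (Protocol, Participants).** Participants are "paired for age, sex and baseline non-verbal intelligence and literacy level (by TOFLHA", and then "within each pair, one cluster is randomized to receive the intervention (n=60), and the other cluster receives the placebo (n=60".
- **Intervention (Protocol, Literacy training).** Of the intervention classes it says: "They will receive literacy training based on analytical and phonemic methods for enabling reading and writing". The control classes cover other subjects, "including geography, history, informatics, and sciences, but no literacy-training". Testing is repeated at 6 months, when training ends.
- **Analysis (SAP).** The primary outcome is the change in free recall of 16 figures. The secondary outcome is the change in hippocampal-prefrontal connectivity. Each is compared by a paired t-test. Age is the only covariate named, and only for connectivity. No literacy variable enters either analysis.

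**The concern.** The protocol's sentence relies on restriction at entry. Restriction removes the influence of a variable only if the variable is then effectively constant, and stays so until the outcome is measured. Neither condition is met here: the entry rule narrows literacy without fixing it, and the intervention is designed to move it in one arm.

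Two things are at stake. The first is interpretation. A gain on a test that uses letters or reading may come directly from what was taught. A reader told that literacy has been dealt with could take such a gain for wider cognitive benefit, and the direction favours the intervention. The second is precision. Baseline TOFHLA was thought important enough to match on, yet the SAP makes no explicit use of it, and dropout will break some of the matched pairs that carry that information.

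**Working it through.** **Does the stated reason hold at baseline?** Only in part. The criterion is a ceiling, so literacy can differ among those who enter. Pairing on TOFHLA would serve no purpose if it did not. The documents do not give the distribution of TOFHLA below the ceiling, so the spread is unknown.

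**Does it hold at 6 months?** No. One arm has had six months of literacy teaching and the other has had none. If training works, participants no longer share a low literacy level when the outcome is measured.

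**Is the arm comparison biased as a result?** No. Baseline literacy is handled by the entry limit, pairing on TOFHLA and randomisation within pairs. Change scores also subtract any stable effect of literacy on the level of a score. Literacy gained after randomisation is a consequence of treatment and part of its effect.

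**How much of the matching survives dropout?** The protocol's own figure comes first: 120 × (1 − 0.20) = 96 completers, which reproduces, or 48 per arm if losses are equal. If dropout is 20% and independent within pairs (assumption), the number of intact pairs is 60 × 0.8 × 0.8 = 38.4, about 38 of 60. These hold 2 × 38.4 = 76.8, about 77 of the 96 completers. The other 19 or so have lost their match. The planned comparison of dropouts with those who continue covers intelligence and sociodemographic features and does not name literacy.

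**What could adjustment be worth?** The documents give no alpha, power, effect size or SD, so this is an illustration.

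- Inputs: 48 per arm (from the protocol's 96), two-sided 5%, 80% power, unpaired t-test (all three assumed).
- Normal approximation: (1.960 + 0.842) × √(2/48) = 2.802 × 0.204 = 0.572 SD of the change score. The t distribution gives 0.578.
- With covariates explaining a share R² of the variance of the change score, the detectable effect is 0.578 × √(1 − R²), and the equivalent number of unadjusted completers is 96/(1 − R²).

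| R² (assumed) | Detectable effect (SD) | Equivalent unadjusted completers |
|---|---|---|
| 0 | 0.578 | 96 |
| 0.10 | 0.578 × 0.949 = 0.548 | 96/0.90 = 107 |
| 0.20 | 0.578 × 0.894 = 0.517 | 96/0.80 = 120 |

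Here R² stands for all four matching factors together (TOFHLA, age, sex, non-verbal intelligence), and for variance of the change, not of the level. TOFHLA alone would give less. So would a comparison against a t-test on intact matched pairs, which already removes variance shared within pairs. The SAP does not say what its paired test is paired on.

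**The case against.** The strongest reply is that literacy is controlled where control is needed. Restriction, matching on TOFHLA, randomisation within pairs and change scores all act at baseline. Literacy acquired later is the intervention working, not a nuisance to be removed. The two SAP outcomes are picture recall and connectivity, and neither is a reading task. The reading and letter-naming tests do not appear in the SAP, and nothing in either document plans to present gains on them as cognitive benefit. Leaving a baseline covariate out of a randomised, matched comparison is not an error, and the assumed R² has no anchor in the documents.

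Most of this stands. A reader might infer from the faulty sentence that literacy is uncontrolled and the arm comparison confounded. The documents do not support that, for the reasons just given. A reader might also infer that the primary result is inflated by reading skill. No route for that is shown: the test uses figures. It does remain true that the protocol itself lists this test among those affected by literacy.

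The reply does not rescue the sentence, which gives a reason that fails at the time the outcome is measured. Nor does it meet the point that a matching factor already collected is left out of both models while some pairs are expected to be broken.

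**Conclusion.** The protocol's assurance is partial at baseline and does not apply at 6 months. The randomised comparison still validly estimates the effect of training on each score. What needs care is the meaning given to a score gain, above all on tests that draw on taught skills, and the unused precision in the matching factors.

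The size cannot be established from the documents. Under an assumed R² of 10-20% for all four factors, the detectable effect falls from 0.58 to 0.55-0.52 SD against an unpaired, unadjusted t-test, and by less for TOFHLA alone or against an intact-pair analysis. The count of about 38 intact pairs assumes dropout is independent within pairs. The contribution of direct teaching to the letter- and reading-based tests cannot be sized. This is a low-cost improvement, not a threat to the trial's validity.

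**What to change.** 1. In the protocol, limit the sentence to comparability of the arms at baseline, and drop the claim that the literacy effect is thereby accounted for.
2. In the SAP, include baseline TOFHLA, preferably with age, sex and non-verbal intelligence, as covariates in the between-arm models for the primary and connectivity outcomes. Do not adjust these models for literacy at follow-up: it is a post-randomisation variable, and conditioning on it would remove part of the treatment effect.
3. State in advance that the reading test and rapid letter naming will be reported as checks that literacy was acquired, not as evidence of wider cognitive benefit.

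The cost is wording in both documents and up to four degrees of freedom in the primary model (three more in the connectivity model, which already has age). No new data are needed. The covariates are baseline measures that the matching already uses.

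Separately, the protocol's two statements of the TOFHLA limit differ on whether a score of exactly 53 counts, and they must be reconciled.
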